3.2 Primary Endpoints

Part 1: Primary Safety Endpoint

The proportion of participants in each cohort who experience at least one Grade 3 or higher adverse event during study participation.

Part 2: Primary Efficacy Endpoint

Disease response at 48 weeks, defined as percent improvement in the IgG4-RD RI score over baseline.

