3.5.2 IgG4-RD Responder Index

The IgG4-RD RI is based on the Birmingham Vasculitis Activity Score for Wegener's Granulomatosis [32], utilized for the evaluation and licensure of rituximab in antineutrophil cytoplasmic antibody (ANCA)-associated vasculitis [33]. The IgG4-RD RI detects change in disease activity and identifies improvements and worsening in the same or different organ systems. The IgG4-RD RI has been used in prior clinical trials to monitor IgG4-RD disease activity [11, 18, 34].

During Part 1A, disease activity will be measured by the IgG4-RD RI at Screening, Baseline/Day 0 if necessary, and at Week 24. During Part 1B and 2, disease activity will be measured by the IgG4-RD RI at Screening, Baseline/Day 0 if necessary, and at Week 48. The IgG4-RD RI does not need to be repeated at Baseline unless there has been a change in Prednisone or other DMARD or if there has been an apparent change in disease activity between Screening and Baseline. The RI will also be measured at any interim visit conducted because of the possibility of recurrent disease or for the purpose of assessing a potential AE.

Imaging required to complete a full IgG4-RD RI assessment will be performed at the Screening visit. Specifically, all participants will undergo either a CT or MRI of the chest, abdomen, and pelvis within 6 weeks of the Screening visit. Participants with clinical evidence of orbital disease will also undergo CT or MRI of that area. If abnormalities in a particular area are detected at Screening, the participant will have the same type of study repeated at Week 24 (Part 1A) or Week 48 (Part 1B and 2) unless there are contraindications to use of the same imaging technique. Imaging at Week 24 (Part 1A) and Week 48 (Part 1B and 2) will be performed if there is a clinical reason to suspect disease activity at that site. Imaging may also be repeated at the discretion of the investigator at a visit other than those two time points if required to assess disease activity because of a potential disease flare or to assess an adverse event. If

participants have received prednisone or another glucocorticoid agent for a total of more than 21 days in the interval between the time of qualifying imaging and the Screening visit, the imaging will be repeated at Screening.

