13.4.2 Primary Analysis of Primary Endpoint

Part 1

Descriptive statistics will be used to summarize the proportion of participants in each cohort who experience at least one Grade 3 or greater adverse event during study participation for all participants in the safety population. The primary analysis of efficacy and safety endpoints will be conducted after all participants in Cohort 1a and 1b complete the Week 48 assessments or are withdrawn from the study.

Part 2

The primary endpoint for Part 2 is disease response at 48 weeks, defined as the percent improvement in the IgG4-RD RI score over baseline:

$$\% \text{ Improvement in IgG4RD RI}_{\text{Week 48}} = 100 * \left(\frac{\text{IgG4RDRI}_{\text{Baseline}} - \text{IgG4RDRI}_{\text{Week 48}}}{\text{IgG4RDRI}_{\text{Baseline}}} \right)$$

For participants whose IgG4-RD RI score is worse (e.g. higher) at week 48 than baseline, their % Improvement in IgG4-RD RI_{Week 48} will be considered 0%. Additionally, participants who use glucocorticoids or other immunosuppressants beyond that permitted by protocol, or who experience a disease flare as defined in Section 3.5.3 at any time point before 48 weeks will be defined as achieving no disease response (0%).

The observed levels of disease response at 48 weeks will be summarized by arm in the mITT population as the median, interquartile range, and range. A between-group comparison of the assessment of disease response at 48 weeks will be performed using a Wilcoxon-Mann-Whitney test with a two-sided Type I α of 0.05, and will be reported with a two-sided 95% confidence interval for the Mann-Whitney parameter (Section 13.6) derived under the proportional odds assumption [41]. The primary analysis of disease response will treat all participants who drop out of the study prior to reaching week 48 for any reason, including a disease flare, initiation of non-protocol therapy, or any other reason to cause them to be unevaluable using the IgG4 Responder Index, as having no disease response (0% improvement) for the primary endpoint. The primary analysis will be conducted after all participants in Cohort 2 complete the Week 48 assessments or are withdrawn from the study.

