20.3 Appendix 3: IgG4-RD RI

Date: ____ / ____ / ____ Visit: _____ Patient ID: _____

IgG4-RD Responder Index (Version: July 25, 2016)**Scoring Rules**Scoring refers to manifestations of disease activity present in the last 28 days

At the initial assessment, the physician enters a 2 after any active organs/sites and a 0 after uninvolved organs/sites.

At each subsequent assessment, the physician enters a 0-3 score after the organ/site listed.

0 = Normal or resolved

1 = Improved but still present since the previous assessment or improved from initial assessment with no change from previous assessment

2 = Disease activity unchanged from previous assessment

Once an organ or site has improved or worsened, the score of 2 will no longer be used for that organ/site, ie, an improved organ/system will maintain a score of 1 until resolution (score as 0) or worsening (score as 3).

No change from previous assessment will often refer to disease manifestations that require follow-up imaging to assess accurately; ie, a disease manifestation only assessable by imaging will be assumed to be unchanged until such time that repeat imaging demonstrates improvement, worsening, or resolution.

3 = Worsened or new disease manifestation since the last assessment and requirement for additional therapy (intent to treat)

Definitions*Organ/Site score:* The overall level of IgG4-RD activity within a specific organ system*Symptomatic:* Is the disease manifestation in a particular organ system symptomatic? (Y = yes; N = no)*Urgent disease:* Disease that requires treatment immediately to prevent serious organ dysfunction (Y = yes; N = no)(Presence of *urgent disease* within an organ leads to **DOUBLING** of that organ system score)*Damage:* Organ dysfunction that has occurred as a result of IgG4-RD and is considered permanent (Y = yes; N = no)

Organ/Site	Activity			Damage	
	organ/site score	Symptomatic (Y/N)	Urgent (Y/N)	Yes/No	Symptomatic (Y/N)
Meninges					
Pituitary Gland					
Orbital lesion (specify location): _____					
Lacrimal Glands					
Parotid Glands					
Submandibular Glands					
Other Salivary Glands (specify): _____					
Mastoiditis/Middle Ear Disease					
Nasal Cavity Lesions					
Sinusitis					
Other ENT Lesions (example: tonsillitis, pharyngitis): _____					
Thyroid					
Lungs					

SAMPLE

Date: ___ / ___ / ___		Visit: ___		Patient ID: ___		
Organ/Site		organ/site score	Activity		Damage	

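### The Week 48 RI is scored against the previous RI, so an unscheduled interim RI can change the primary-endpoint score of an organ in the same disease state; the plan should fix baseline as the comparator

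*Combined protocol and SAP*

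**What the plan says.** Section 13.4.2 states: "The primary endpoint for Part 2 is disease response at 48 weeks, defined as the percent improvement in the IgG4-RD RI score over baseline". The same section sets a participant to 0% if the RI is worse than baseline, if a flare occurs or non-protocol immunosuppression is used before 48 weeks, or if the participant drops out.

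For Parts 1B and 2, Section 3.5.2 says that "disease activity will be measured by the IgG4-RD RI at Screening, Baseline/Day 0 if necessary, and at Week 48". It also requires the RI to be "measured at any interim visit conducted because of the possibility of recurrent disease or for the purpose of assessing a potential AE". The schedule in Appendix 1 agrees: after baseline the RI appears only at Week 48 and at unscheduled visits.

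The form in Appendix 3 works as follows:

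- **First RI:** "At the initial assessment, the physician enters a 2 after any active organs/sites and a 0 after uninvolved organs/sites".
- **Score 0:** normal or resolved.
- **Score 1:** improved since the previous RI, or improved from the initial RI and stable since the previous one.
- **Score 2:** unchanged from the previous RI. However, "Once an organ or site has improved or worsened, the score of 2 will no longer be used for that organ/site"; the sentence goes on to say that an improved organ stays at 1 until it resolves (0) or worsens (3).
- **Score 3:** "3 = Worsened or new disease manifestation since the last assessment and requirement for additional therapy (intent to treat".
- **Imaging rule:** an organ that can be judged only by imaging counts as unchanged until imaging is repeated.

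No section says that Week 48 is to be scored against baseline, or that interim RIs are to be ignored.

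**The concern.** The endpoint is defined against baseline, but the instrument that supplies it is mostly defined against the last RI performed. For a participant with no interim RI the two coincide. For a participant with one, the Week 48 comparator is an ad hoc visit triggered by something that happened after randomization. Two participants in the same state at Week 48 can then receive different values.

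The course that exposes this is plausible. The prednisone taper in Section 7.1.1.3 ends at Day 69, about 38 weeks before Week 48 ((336 − 69)/7 = 38.1), and Section 1.1.2 describes frequent relapse once glucocorticoids are tapered or stopped. An adverse-event visit during or soon after the taper could record steroid-induced improvement that has gone by Week 48. What is at stake is the meaning of the primary endpoint and of the 50% and 75% response endpoints. Complete remission is less exposed, because an organ resolved at Week 48 scores 0 whatever its history.

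**Working it through.** **The plan's own figures.** Section 13.7 uses Noether's formula with allocation fraction c = 2/3, δ = 0.75 and 90% power: N = (1.960 + 1.282)² / [12 × (2/3) × (1/3) × 0.25²] = 63.04, against 63 stated. Power at 63 is 0.8998. The Fisher power for 25% v 65% with 21 and 42 participants is 0.826, as stated. None of these is in question.

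**One organ, form applied literally.** The organ scores 2 at baseline, improves, and is back at its baseline extent at Week 48 with no additional therapy required.

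- No interim RI: unchanged from the previous RI (baseline), so score 2.
- Interim RI recorded as 1: score 2 is barred, and score 3 also needs a requirement for therapy, so score 1 is kept. A site relying on the clause that sends a worsened organ to 3 would enter 3.

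**Participant level.** The minimum eligible RI is 4 (Section 4.1). Assume two non-urgent organs scoring 2 each, with organ A resolved (0) at Week 48 and organ B as above. Improvement = 100 × (4 − Week 48 RI)/4.

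| Organ B at Week 48 | RI | Improvement |
|---|---|---|
| 2 (no interim RI) | 2 | 50% |
| 1 (interim RI, score kept) | 1 | 75% |
| 3 (interim RI, not treated as a flare) | 3 | 25% |

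If both organs follow organ B's course, the RI is 4 without an interim RI (0%), 2 if both keep score 1 (50%), and 6 if both are scored 3 (floored at 0%).

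One organ point is worth 100/baseline RI: 25 percentage points at RI 4, 16.7 at 6, 12.5 at 8 and 8.3 at 12.

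**How general is it?** I crossed five organ states at Week 48 (resolved, much better, somewhat better, baseline level, worse) with therapy required or not at that visit, and with six interim situations (the same five states, with worse split by need for therapy). That gives 5 × 2 × 6 = 60 combinations.

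- In 41 the Week 48 score is the same with and without the interim RI. These include every steadily improving, stable-after-improvement or resolved course.
- In 19 it differs, or no code fits. All involve a non-monotone course or worsening. Three of the 19 are overridden because therapy required at the interim visit makes the participant a flare, hence 0%.

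These are counts of cases, not probabilities, and they do not apply the imaging rule, which narrows the effect further.

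**Illustrative simulation, no drug effect on disease.** Every frequency is an assumption: 2–6 organs; each resolved 35%, improved 50% or unchanged 15% after the taper; 30% or 60% of improved organs back at baseline extent without therapy; 35% of participants flare and score 0%.

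| Organs returning | Mean improvement, no interim RI | Interim RI, score 1 kept | Interim RI, score 3 given |
|---|---|---|---|
| 30% | 34% | 39% | 30% |
| 60% | 29% | 39% | 22% |

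- Interim RIs in 50–70% of elotuzumab and 25–30% of placebo participants: δ is 0.51–0.54 if score 1 is kept, and 0.47–0.49 if score 3 is given.
- Score 1 kept, interim RIs in 30% of elotuzumab and 50% of placebo participants: δ is 0.48–0.49.
- First pattern, score 1 kept, only 5–10% of organs returning: δ is about 0.50–0.51.

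At δ = 0.54, √(63 × 12 × 2/9) × 0.04 = 0.518, so the rejection probability is Φ(0.518 − 1.96) + Φ(−0.518 − 1.96) ≈ 8%, against a nominal 5%.

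**The case against.** The strongest reply is that little is left once the plan's other rules are applied. Recurrence that calls for extra immunosuppression is a flare under Section 3.5.3 and scores 0% if it occurs before 48 weeks. Organs judged only by imaging stay at 2 unless imaging is repeated, and interim imaging is discretionary. Section 8.2 leaves non-flare unscheduled visits to clinical judgement, so an RI at every adverse-event visit is not assured, although Section 3.5.2 requires one. The form is dated and cited as validated, and altering it has a cost. All of this stands and limits the scope. It does not remove the problem for organs that can be examined directly, or for adverse-event and false-alarm recurrence visits that leave the participant in the analysis.

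A reader might infer that the rule favours elotuzumab, because Section 5.1.3 reports more infections with elotuzumab in myeloma (81.4% v 74.4%) and adverse-event visits may be commoner on the active arm. The documents do not support that. Suspected recurrence also triggers an RI and could be commoner on placebo. The clause that sends a worsened organ to 3 supports a reading that reverses the sign. No visit frequencies are given.

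A reader might also infer that any interim RI alters the Week 48 score, or that the usual effect is 50 points. Neither follows: most combinations in the grid are unaffected, and one organ point moves a participant by 8.3 to 25 points over baseline RI 12 to 4.

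**Conclusion.** The point holds in limited form. The form's stated rules, combined with unscheduled RIs and no named comparator, let one Week 48 disease state yield 50%, 75% or 25% improvement at baseline RI 4. The affected participants are those with a non-monotone course who are not already set to 0%, and the affected organs are those assessable without imaging or re-imaged at the interim visit. The 25% result also assumes that recurrence first found at Week 48 is not counted as a flare; Section 13.4.2 covers flares before 48 weeks and leaves that visit open.

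How often this will happen, and which arm it would favour, cannot be derived from the documents. The largest simulated shift, δ = 0.54 under assumed frequencies, is small beside the 0.75 target, and the sample size is unaffected. This is a cheap improvement to the endpoint's definition, not a threat to the trial's validity.

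**What to change.** Add to Section 13.4.2, and as a study-specific note to Appendix 3, wording to this effect:

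*For the Week 48 RI used in the primary and the 50% and 75% response endpoints, each organ is scored against the baseline RI regardless of any interim RI: 0 resolved; 1 improved from baseline; 2 not improved from baseline; 3 worse than baseline or new, and requiring additional therapy. Recurrence first found at the Week 48 visit that meets the Section 3.5.3 flare definition is handled under the 0% rule. Interim RIs are used only to document flares and adverse events.*

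This matches the endpoint's own definition. In the worked example, if the recurrence is not a flare, it gives 50% whether or not an interim RI was done. It also gives a code to an existing organ that is worse without needing therapy, which the form lacks. The note should say as well how a new manifestation not requiring therapy is coded, since neither the form nor this wording settles it.

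Cost: a short addition to the plan and an eCRF completion note, with no new data and no change to N = 63. The downside is a one-visit departure from the form's previous-assessment wording, which should be declared when the results are reported.

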20.4 Appendix 4: PhGA and PGA VAS

PATIENT GLOBAL ASSESSMENT:
(100mm)

Patient Instructions: Please answer the question by placing a vertical (|) mark to indicate your response. Please sign and date this form.

Considering all the ways IgG4 Related Disease affects you, mark a vertical line at the spot on the horizontal line to describe your disease activity within the last 24 hours.

YOUR RESPONSE:

Patient's Signature:

Date:

PHYSICIAN GLOBAL ASSESSMENT:

(100mm)

Subject ID #: _____**Assessment Date:** _____ / _____ / _____
(dd/month/year)**YOUR RESPONSE:**

Please rate the patient's current IgG4 Related Disease activity on the scale below, with 0 being no disease activity and 100 being extremely active disease activity.

Initials of individual marking the line: _____

Date: _____
(dd/month/year)**For Site Coordinator Use Only**

Site Coordinator Directions: Using the markings provided, measure from the "0" to the vertical line placed by the physician. Enter the distance in millimeters as indicated below, then transfer the pertinent information onto the appropriate eCRF page, and place this document in the subject's research record.

Length of line
(from 0 to vertical assessment line) _____ mm

Initials of site personnel measuring the line: _____

Date: _____
(dd/month/year)

20.5 Appendix 5: Flare Documentation Guide

AIG01 FLARE DOCUMENTATION GUIDANCE

This document provides guidance with regard to the evaluation of potential disease flares and outlines appropriate work-ups for IgG4-RD activity in each organ.

Investigators will complete a disease activity assessment only in the organs involved in the flare. The suggested laboratory evaluation, radiology studies, and other procedures (e.g., biopsy) as well as the minimum criteria for diagnosis of a disease flare are provided for each organ system.

Following the documentation of evidence supporting a flare in a given organ, the investigator will complete a short narrative justifying the diagnosis of a flare in that organ.

Collection of data during evaluation of a potential disease flare

For each potential flare event, the following will be collected:

1. Observation that led to the initiation of evaluation for a disease flare (mark all that apply)

- New/worsening symptoms reported by the patient
- New/worsening finding on physical examination
- New/worsening laboratory finding
- Incidental finding on imaging

2. Investigator Narrative (free text)

The narrative should be a complete medical account of the event. The narrative should include a description of any symptoms, physical examination findings, laboratory abnormalities, imaging findings, or biopsy data collected for the evaluation of this event.

The narrative should refer to historical data (e.g., the patient's baseline visit or more recent trial visit) to establish the new/worsening nature of the disease manifestations.

The descriptions must be sufficiently detailed to understand the findings and the investigator's interpretation of them. The narrative must describe findings in every organ affected by the disease flare. Data supporting the occurrence of a disease flare in each organ are recorded in the organ-specific sections, below.

After the completion of treatment, the narrative should be updated with response to treatment.

3. Details on the organ-specific flare criteria must be completed for every organ potentially affected by the disease flare.

SAMPLE

4. Treatment (mark all that apply)

- Glucocorticoids (specify drug, dose, start/stop dates)
- Supportive therapy (e.g., pancreatic enzyme replacement, bile acid sequestrant, artificial saliva/lubricant, specifying drug, dose, start/stop dates)
- Immunosuppression other than glucocorticoids (specify drug, dose, start/stop dates)
- Surgical intervention or other procedural intervention (e.g., stenting), specify procedure and date performed (describe in narrative)
- None (provide rationale in the investigator narrative)

5. Outcome of treatment: (Mark all that apply)

- Returned to baseline before current flare
- Disease activity suppressed but disease damage sustained (resultant organ damage compared to pre-flare baseline)
- Ongoing immunosuppressive therapy required at 24-weeks

ORGAN-SPECIFIC FLARE CRITERIA

Pachymeninges

Symptoms and Findings

Symptom(s)	Observed (✓)	New onset or worsening (N/W)	Description
Symptoms consistent with pachymeningeal flare:			Describe the finding and indicate why it represents IgG4-RD activity worsening from recent baseline
Headache			
Systemic/constitutional			
Other (describe)			
None			
Physical examination findings consistent with pachymeningeal flare			Describe the finding and indicate why it represents IgG4-RD activity worsening from recent baseline
Cranial nerve palsy, neurologic abnormalities consistent with radiculomyelopathy			
Other (describe)			
None			
Laboratory findings consistent with pachymeningeal flare			Describe the finding and indicate why it represents IgG4-RD activity worsening from recent baseline
Cerebrospinal fluid pleocytosis			
Cerebrospinal fluid increased protein			
Other (describe)			
None			
Imaging (CT, MRI, PET) consistent with pachymeningeal flare			Describe the finding and indicate why it represents IgG4-RD activity worsening from recent baseline
 Meningeal enhancement  Meningeal thickening			

Symptom(s)	Observed (✓)	New onset or worsening (N/W)	Description
Other (describe)			
None			
Biopsy results consistent with pachymeningeal flare			Describe tissue and reading
Biopsy/tissue consistent with pachymeningeal flare			
Biopsy/tissue not done or insufficient			
Not consistent, specify tissue and reading			

Criteria for Pachymeningitis Flare and Investigator Conclusion

Criteria for Flare	Present (✓)	Absent (✓)
Required to be present:		
1. New or worsening symptom or physical examination finding consistent with IgG4-RD pachymeningitis		
2. EITHER:		
a. Cerebrospinal fluid lab finding consistent with IgG4-RD pachymeningitis OR		
b. Imaging finding confirming new or worsening meningeal involvement		
Required to be absent:		
Alternative diagnosis or inconsistent biopsy finding		

Investigator Conclusion – Pachymeningitis Flare

Yes

No

Why do you believe this patient is having an IgG4-RD flare involving the pachymeninges?

Pituitary Gland

Symptoms and Findings

Symptom(s)	Observed (✓)	New onset or worsening (N/W)	Descriptions
Symptoms consistent with pituitary flare			Describe the finding and indicate why it represents IgG4-RD activity worsening from recent baseline
Visual field abnormalities, headache, symptoms consistent with anterior or posterior pituitary endocrine failure			
Systemic/constitutional			
Other (describe)			
None			
Physical examination findings consistent with pituitary flare			Describe the finding and indicate why it represents IgG4-RD activity worsening from recent baseline
Visual field deficits			
Other (describe)			
None			
Laboratory findings consistent with pituitary flare			Describe the finding and indicate why it represents IgG4-RD activity worsening from recent baseline
Pituitary endocrine dysfunction, documented by abnormalities of one or more of the following: 
 Thyroid stimulating hormone Growth hormone Follicular stimulating hormone Luteinizing hormone Cortisol Prolactin 			

Symptom(s)	Observed (✓)	New onset or worsening (N/W)	Descriptions
Anti-diuretic hormone			
Other (describe)			
None			
Other, describe: Imaging (CT, MRI, PET) consistent with pituitary flare			Describe the finding and indicate why it represents IgG4-RD activity worsening from recent baseline
 Pituitary mass  Pituitary enhancement			
Other (describe)			
None			
Biopsy results consistent with pituitary flare			Describe tissue and reading
Biopsy/tissue consistent with pituitary gland flare			
Biopsy/tissue not done or insufficient			
Not consistent, specify tissue and reading			

Criteria for Pituitary Gland Flare

Criteria for Flare	Present (✓)	Absent (✓)
Required to be present:		
EITHER New or worsening anterior/posterior pituitary endocrine dysfunction OR		
Imaging finding confirming new or worsening pituitary involvement		
Required to be absent:		
Alternative diagnosis or inconsistent biopsy findings		

Investigator Conclusion – Flare in Pituitary Gland

Yes

No

Why do you believe this patient is having an IgG4-RD flare involving the pituitary gland?

Orbits**Symptoms and Findings**

Symptom(s) or Finding(s)	Observed (✓)	New onset or worsening (N/W)	Description
Symptoms consistent with flare in orbits:			Describe the finding and indicate why it represents IgG4-RD activity worsening from recent baseline
Diplopia, proptosis, eye or retrobulbar discomfort or pain, or other visual symptoms including vision blurring or loss, symptoms consistent with scleritis, symptoms from compression of peripheral nerves in the area of the orbit, such as trigeminal and infra-orbital nerves (pain or numbness)			
Systemic/constitutional			
Other (describe)			
None			
Physical examination findings consistent with orbital flare			Describe the finding and indicate why it represents IgG4-RD activity worsening from recent baseline
Proptosis, supra-orbital swelling or other peri-orbital swelling consistent with enlargement of extra-ocular muscles, field cuts, cranial nerve palsies, extraocular movement abnormality, infra-orbital/supra-orbital nerve enlargement			
Other (describe)			
None			
Imaging (CT, MRI, PET) consistent with orbital flare			Describe the finding and indicate why it represents IgG4-RD activity worsening from recent baseline
CT or MRI compatible with orbital disease  enlargement of extra-ocular muscles  enlargement of optic nerve  abnormalities of retrobulbar space or within cavernous sinus			

Symptom(s) or Finding(s)	Observed (✓)	New onset or worsening (N/W)	Description
Other (describe)			
None			
Biopsy results consistent with orbital flare			Describe tissue and reading
Biopsy/tissue consistent with orbital flare			
Biopsy/tissue not done or insufficient			
Not consistent, specify tissue and reading			

Criteria for Orbital Flare

Criteria for Flare	Present (✓)	Absent (✓)
Required to be present, EITHER:		
New or worsening symptom or physical examination finding consistent with orbital flare OR		
New or worsening orbital abnormality on imaging consistent with orbital flare		
Required to be absent:		
Alternative diagnosis or inconsistent biopsy findings		

Investigator Conclusion – Flare in the Orbit

Yes
 No

Why do you believe this patient is having an IgG4-RD flare involving the orbit(s)?

Lacrimal Glands

Symptoms and Findings

Symptom(s) or Findings	Observed (✓)	New onset/worsening (N/W)	Description
Symptoms consistent with flare in lacrimal glands			Describe the finding and indicate why it represents IgG4-RD activity worsening from recent baseline
Lacrimal gland discomfort, pain or swelling; redness of the eye, excessive tearing; blurred vision			
Systemic/constitutional			
Other (describe)			
None			
Physical examination findings consistent with lacrimal gland flare			Describe the finding and indicate why it represents IgG4-RD activity worsening from recent baseline
Lacrimal gland swelling/mass			
Other (describe)			
None			
Imaging (CT, MRI, PET) consistent with lacrimal gland flare			Describe the finding and indicate why it represents IgG4-RD activity worsening from recent baseline
 Lacrimal gland enlargement demonstrated by CT or MRI			
Other (describe)			
None			
Biopsy results consistent with lacrimal gland flare			Describe tissue and reading
Biopsy/tissue consistent with lacrimal gland flare			
Biopsy/tissue not done or insufficient			
Not consistent, specify tissue and reading			

Criteria for Lacrimal Gland Flare

Criteria for Flare	Present (✓)	Absent (✓)
Required to be present:		
New or worsening lacrimal gland enlargement/mass on physical examination or observed on imaging		
Required to be absent:		
Alternative diagnosis or inconsistent biopsy findings		

Investigator Conclusion – Lacrimal Gland Flare

Yes
 No

Why do you believe this patient is having an IgG4-RD flare involving the lacrimal glands?

Major Salivary Glands

Specific salivary gland(s) involved:

- Parotid
- Submandibular
- Sublingual

Symptoms and Findings

Symptom(s) or Findings	Observed (✓)	New onset or worsening (N/W)	Description
Symptoms consistent with salivary gland flare			Describe the finding and indicate why it represents IgG4-RD activity worsening from recent baseline
Sicca symptoms, pain, swelling of gland(s)			
Systemic/constitutional			
Other (describe)			
None			
Physical examination findings consistent with salivary gland flare			Describe the finding and indicate why it represents IgG4-RD activity worsening from recent baseline
Salivary gland swelling or tenderness			
Other (describe)			
None			
Imaging (CT, MRI, PET) consistent with salivary gland flare			Describe the finding and indicate why it represents IgG4-RD activity worsening from recent baseline
 Major salivary gland (submandibular, parotid, or sublingual) swelling demonstrated by CT or MRI			
Other (describe)			
None			
Biopsy results consistent with salivary gland flare			Describe tissue and reading
Biopsy/tissue consistent with salivary gland flare			

Symptom(s) or Findings	Observed (✓)	New onset or worsening (N/W)	Description
Biopsy/tissue not done or unreadable			
Not consistent, specify tissue and reading			

Criteria for Salivary Gland Flare

Criteria for Flare	Present (✓)	Absent (✓)
Required to be present:		
New or worsening salivary gland enlargement or tenderness on physical examination or new/worse enlargement on imaging		
Required to be absent:		
Alternative diagnosis or inconsistent biopsy findings		

Investigator Conclusion – Flare in Salivary Gland(s)

Yes
 No

Why do you believe this patient is having a disease flare in one or more of the major salivary glands?

Lymph node(s)**Symptoms and Findings**

Symptom(s) or Findings	Observed (✓)	New onset or worsening (N/W)	Description
Symptoms consistent with flare in lymph node(s)			Describe the finding and indicate why it represents IgG4-RD activity worsening from recent baseline
Patient-reported swelling			
Systemic/constitutional			
Other (describe)			
None			
Physical examination findings consistent with flare in lymph node(s)			Describe the finding and indicate why it represents IgG4-RD activity worsening from recent baseline
Lymphadenopathy (specify localized or diffuse)			
Other (describe)			
None			
Laboratory findings consistent with flare in lymph node(s): NA			
Imaging (CT, MRI, PET) consistent with lymphadenopathy (localized or diffuse)			Describe the finding and indicate why it represents IgG4-RD activity worsening from recent baseline
 Lymphadenopathy demonstrated by imaging			
Other (describe)			
None			
Biopsy results consistent with lymph node flare			Describe tissue and reading
Biopsy/tissue consistent with lymph node flare			
Biopsy/tissue not done or unreadable			
Not consistent, specify tissue and reading			

Criteria for Lymph Node Flare

Criteria for Flare	Present (✓)	Absent (✓)
Required to be present, EITHER:		
In a patient with concurrent IgG4-RD in another organ(s): Multiple enlarged nodes (generally nontender) by physical examination or imaging in an area separate from other current organ with flare OR		
In a patient with no other organ with concurrent flare: Multiple enlarged lymph nodes (generally nontender) by physical examination or imaging AND lymph node biopsy to exclude other diagnosis, such as malignancy		
Required to be absent:		
Alternative diagnosis or inconsistent biopsy findings		

Investigator Conclusion – Flare in Lymph Node(s)

Yes
 No

Why do you believe this patient is having an IgG4-RD flare manifested as lymphadenopathy?

Lungs, Including Pleura and Parenchyma**Symptoms and Findings**

Symptom(s) or Findings	Observed (✓)	New onset or worsening (N/W)	Description
Symptoms consistent with lung flare			Describe the finding and indicate why it represents IgG4-RD activity worsening from recent baseline
Dyspnea at rest or with exertion, cough			
Systemic/constitutional			
Other (describe)			
None			
Physical examination findings consistent with lung flare			Describe the finding and indicate why it represents IgG4-RD activity worsening from recent baseline
Increased respiratory rate, findings suggestive of pleural effusion, dry crackles compatible with pulmonary fibrosis, localized diminished breath sounds, findings consistent with infiltrate			
Other (describe)			
None			
Laboratory findings consistent with lung flare			Describe the finding and indicate why it represents IgG4-RD activity worsening from recent baseline
New or worsening pulmonary function test abnormalities consistent with lung flare			
Other (describe)			
None			
Imaging (CXR, CT, MRI, PET) consistent with lung flare			Describe the finding and indicate why it represents IgG4-RD activity worsening from recent baseline
 Pulmonary nodules or mass  Pulmonary infiltrate/ground glass opacities consistent with interstitial pneumonia  Pulmonary fibrosis			

Symptom(s) or Findings	Observed (✓)	New onset or worsening (N/W)	Description
 Pleural effusion  Pleural thickening  Peribronchovascular and septal thickening  Paravertebral mass/Paravertebral band-like soft tissue in thorax			
Other (describe)			
None			
Biopsy results consistent with lung flare			Describe tissue and reading
Biopsy/tissue consistent with lung flare			
Biopsy/tissue not done or unreadable			
Not consistent, specify tissue and reading			

Criteria for Parenchymal or Pleural Lung Flare

Criteria for Flare	Present (✓)	Absent (✓)
Required to be present:		
New or worsening imaging finding confirming pleuropulmonary involvement		
Required to be absent:		
Alternative diagnosis or inconsistent biopsy findings		

Investigator Conclusion – Lung Flare

Yes
 No

Why do you believe this patient is having an IgG4-RD flare in the lungs or pleura?

Aorta & large blood vessels**Symptoms and Findings**

Symptom(s) or Findings	Observed (✓)	New onset or worsening (N/W)	Description
Symptoms consistent with aorta & large blood vessels flare			Describe the finding and indicate why it represents IgG4-RD activity worsening from recent baseline
Pain, palpable mass			
Systemic/constitutional			
Other (describe)			
None			
Physical examination findings consistent with aorta & large blood vessels flare			Describe the finding and indicate why it represents IgG4-RD activity worsening from recent baseline
Palpable arterial mass, especially if pulsatile, or bruit			
Other (describe)			
None			
Imaging (CT, MRI, PET) consistent with aorta & large blood vessels flare:			Describe the finding and indicate why it represents IgG4-RD activity worsening from recent baseline
 Aneurysm  Dissection  Thickening/enhancement of vessel wall			
Other (describe)			
None			
Biopsy results consistent with aorta/large blood vessel flare			Describe tissue and reading
Biopsy/tissue consistent with aorta/large blood vessel flare			
Biopsy/tissue not done or unreadable			
Not consistent, specify tissue and reading			

Criteria for Aorta & Large Blood Vessel Flare

Criteria for Flare	Present (✓)	Absent (✓)
Required to be present: EITHER		
New or worsening aortic or other vessel wall thickening or other evidence of aortitis (dissection, aneurysm) by imaging		
Demonstration of aortitis, dissection or aneurysm or similar findings for other large artery at surgery or intervention (stenting) of an aneurysm, dissection or other vascular anomaly		
Required to be absent:		
Alternative diagnosis or inconsistent biopsy findings		

Investigator Conclusion – Aorta & Large Blood Vessel Flare

Yes
 No

Why do you believe this patient is having an IgG4-RD flare manifested by involvement of the aorta or other large blood vessels?

Retroperitoneum, Mediastinum, & Mesentery**Symptoms and Findings**

Symptom(s) or Findings	Observed (✓)	New onset or worsening (N/W)	Description
Symptoms consistent with retroperitoneum, mediastinum & mesentery flare			Describe the finding and indicate why it represents IgG4-RD activity worsening from recent baseline
Pain (e.g., flank, back, thighs, abdominal, other including chronic pain), leg edema, dyspnea, cough			
Systemic/constitutional			
Other (describe)			
None			
Physical examination findings consistent with retroperitoneum, mediastinum & mesentery flare			Describe the finding and indicate why it represents IgG4-RD activity worsening from recent baseline
Palpable mass or findings consistent with superior vena cava syndrome, leg edema, or fibrosing mediastinitis			
Other (describe)			
None			
Laboratory findings consistent with retroperitoneum, mediastinum & mesentery flare			
For retroperitoneal involvement of ureters: elevated creatinine, decreased eGFR			
Other (describe)			
None			
Imaging (CT, MRI, PET) consistent with retroperitoneum, mediastinum & mesentery flare			Describe the finding and indicate why it represents IgG4-RD activity worsening from recent baseline
 Mass lesion			

Symptom(s) or Findings	Observed (✓)	New onset or worsening (N/W)	Description
 Ureteral stenosis or hydronephrosis  Superior vena cava syndrome  Retroperitoneal enhancement (often infrarenal, peri-aortic distribution extending down to iliac vessels but may involve root of mesentery)  Circumferential/antero-lateral soft tissue around infrarenal aorta or iliac arteries  Other radiologic evidence of inflammation in mesentery or mediastinum			
Other (describe)			
None			
Biopsy results consistent with retroperitoneum, mediastinum & mesentery flare			Describe tissue and reading
Biopsy/tissue consistent with retroperitoneum, mediastinum & mesentery flare			
Biopsy/tissue not done or unreadable			
Not consistent, specify tissue and reading			

Criteria for Flare in Retroperitoneum, Mediastinum or Mesentery

Criteria for Flare	Present (✓)	Absent (✓)
Required to be present: EITHER		
New or worsening imaging evidence of involvement of retroperitoneum, mediastinum and/or mesentery		
Tissue confirmation at time of surgery or intervention (stenting) that confirms involvement of retroperitoneum, mediastinum and/or mesentery		
Required to be absent:		

Criteria for Flare	Present ()	Absent ()
Alternative diagnosis or inconsistent biopsy findings		

Investigator Conclusion – Flare in Retroperitoneum, Mediastinum or Mesentery Yes No

Why do you believe this patient is having an IgG4-RD flare involving the retroperitoneum, mediastinum, or mesentery?

Pancreas and Common Bile Duct**Symptoms and Findings**

